11.3 Statistical analysis

11.3.1 Efficacy analysis

Treatment and analysis will be performed on the worst of the two eyes at diagnosis. Worst eye will be defined based on TBUT or, in case of identical TBUT between the two eyes, OXFORD class. In case of identical TBUT and OXFORD class, NIBUT will be considered.

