1.3 Devices under study

The drug in the study is oral doxycycline, which is the most commonly used oral tetracycline for treating posterior blepharitis and MGD. The rationale for using tetracyclines is based in part on small clinical trials that have reported the drugs' effectiveness in improving symptoms in patients with ocular rosacea and in improving tear break-up time in patients with rosacea and MGD. [1]

Doxycycline is a metal ion chelator and a broad-spectrum antibiotic that prevents access of acyl t-RNA to the acceptor site on the mRNA-30s ribosomal subunit complex. In addition to these established functions, other properties that have recently been ascribed to

Clinical Trial Protocol CPDOXY1

Comparison between continuous and pulsed oral doxycycline treatment protocols for refractory meibomian gland dysfunction - 9 months follow-up prospective study

doxycycline include differential inhibition of the activity of members of the matrix metalloproteinase (MMP) family, inhibition of MMP synthesis, inhibition of interleukin-1 synthesis, inhibition of activated B cell function, inhibition of nitric oxide (NO) synthesis by lipopolysaccharide activated macrophages, and inhibition of collagen synthesis by cultured chondrocytes. [3]

Tetracyclines also decrease lipase production in both *S. epidermidis* and *S. aureus*. However, it's worth noting that tetracyclines can cause photosensitization, gastrointestinal upset, vaginitis, and, rarely, azotemia. Tetracyclines have been implicated in cases of pseudotumor cerebri, and their metabolism may alter the effectiveness of certain medications (e.g., decrease the effectiveness of oral contraceptives and potentiate the effect of warfarin). Tetracyclines are contraindicated in pregnancy, for nursing women, and for patients with a history of hypersensitivity to tetracyclines. Furthermore, tetracyclines should not be used in children under 8 years of age since staining of teeth may occur; however, oral erythromycin may be used as an alternative. [1-2-3]

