5.2 Secondary endpoints

The study's secondary endpoints are the Low- and high-tech anterior segment parameters (NIBUT, TBUT, Oxford class).

For these parameters, the changes occurring in the two groups at each visit compared to baseline will also be evaluated.

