8. STUDY ASSESSMENTS/VISITS

8.1 Study visits:

The study comprises three visits: Visit 1 (baseline), Visit 2 (3rd month), and Visit 3 (6th month).

8.2 Study assessments:

At each visit, the following examinations will be performed in both eyes in the following order:

- OSDI questionnaire
- NIBUT
- Schirmer test
- TBUT
- Corneal staining evaluation (Oxford scale)

All above mentioned examinations and all evaluations required by the study are part of the normal clinical practice.

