11.2 Sample size

The sample size estimate was based on a test for before-after studies using a paired t-test, defining a 1-sec change in Break-Up Time as clinically relevant and a standard deviation of 2.3 sec. Setting the error to 2.5% (one-tailed), 43 patients would be required, assuming a power of 80%. Assuming drop out, the final enrollment will be 65 patients.

Clinical Trial Protocol CPDOXY1

Comparison between continuous and pulsed oral doxycycline treatment protocols for refractory meibomian gland dysfunction - 9 months follow-up prospective study

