11.3.1.2 Secondary efficacy endpoints

Paired t-test will be used to study the secondary variables.

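### The analysed eye is picked for its low TBUT and TBUT is then tested before-after, so regression to the mean will look like improvement within each arm unless the eye is chosen on a separate earlier reading

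*Protocol*

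**What the plan says.** Section 11.3.1 of the protocol restricts the efficacy analysis to one eye: "Treatment and analysis will be performed on the worst of the two eyes at diagnosis". It ranks the eyes as follows: "Worst eye will be defined based on TBUT or, in case of identical TBUT between the two eyes, OXFORD class". NIBUT decides if both are tied.

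TBUT, NIBUT and Oxford class are the secondary endpoints in section 5.2, which adds: "For these parameters, the changes occurring in the two groups at each visit compared to baseline will also be evaluated". The only test named for them is in section 11.3.1.2: "Paired t-test will be used to study the secondary variables". Section 11.2 sizes the study on the same kind of test, "defining a 1-sec change in Break-Up Time as clinically relevant", with a standard deviation of 2.3 s.

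Data from the other eye will exist. Section 8.2 states: "At each visit, the following examinations will be performed in both eyes in the following order". Section 1.3 gives the route: "The drug in the study is oral doxycycline". The timetable in section 14.7 has TBUT at Visits 1, 2 and 3 and at no earlier time.

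**The concern.** A TBUT reading contains a lasting part and a part that varies from visit to visit. The eye with the lower reading is, on average, an eye whose transient part happened to be low that day. At the next measurement that part averages out and the reading rises, with or without treatment. If the selecting reading also serves as the before value of a paired test, this rise is counted as improvement.

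Both arms receive doxycycline, so no untreated arm would reveal the artefact. A within-arm TBUT improvement could be reported for a regimen that does nothing to TBUT. Using both eyes, which are already measured, avoids the problem.

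**Working it through.** **1. The plan's own figure.** Section 11.2 gives a 1 s change, SD 2.3 s, one-sided 2.5%, power 80% and 43 patients.

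- Normal approximation: n = ((1.960 + 0.842) × 2.3 / 1)² = 41.5, so 42.
- Noncentral t: power 79.5% at n = 43 and 80.5% at n = 44.

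The stated 43 is therefore reproduced to within one patient, with 2.3 s read as the SD of the paired change. That reading is used below.

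**2. Model with no treatment effect.**

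- If visit errors are independent over time, the SD of change implies a visit-error variance per eye of 2.3² / 2 = 2.645.
- f is the share of that variance common to both eyes at a visit (assumed). Only the unshared part, v = (1 − f) × 2.645, can mislead the choice of eye.
- s is the SD of each eye's lasting departure from the patient's own level (assumed).

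The lower of the two eyes lies on average √((s² + v)/π) below the patient's level. The share v/(s² + v) of that gap is transient and is recovered at the next visit. The expected false gain is the product:

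gain = v / √(π (s² + v))

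Middle setting, f = 0.5 and s = 1: v = 1.3225, so gain = 1.3225 / √(π × 2.3225) = 1.3225 / 2.701 = 0.49 s.

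**3. Range.** The false-positive rates come from 8,000 simulated trials per setting. They count the improvement side at one-sided 2.5%. The two sizes are n = 32 (one arm, about 65/2) and n = 43 (the calculated sample).

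| f | s (s) | False gain (s) | False positives, n = 32 | False positives, n = 43 |
|---|---|---|---|---|
| 0 | 0 | 0.92 | 67% | 79% |
| 0.25 | 1 | 0.65 | 37% | 47% |
| 0.5 | 1 | 0.49 | 22% | 28% |
| 0.5 | 2 | 0.32 | 12% | 14% |
| 0.75 | 1 | 0.29 | 11% | 12% |
| 0.9 | 2 | 0.07 | 3.9% | 3.6% |

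**4. Both eyes instead.** With the mean of the two eyes nothing is selected on TBUT. The expected false gain is 0 s, and the simulated error rate was 2.2 to 2.8% in every setting.

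**5. Between arms.** At f = 0.5, s = 1 and 32 per arm, worst-eye changes compared between two identical arms differ by 0.00 s on average, with 5.3% rejections at two-sided 5%. The bias cancels there.

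**The case against.** **The timing is not certain.** A reader might infer that the protocol explicitly selects the eye on the Visit 1 reading. It does not: section 11.3.1 says *at diagnosis*, and sections 4.1 and 6.2 require two months of first-line therapy before baseline, so diagnosis may precede Visit 1. With an earlier, separate reading, much of the regression would be over by the before value. This stands as a condition on the point. Against it, the protocol schedules no earlier TBUT and does not say which reading is meant.

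**The trial's main question is comparative.** A reader might infer that the primary result is compromised. It is not. OSDI is a patient-level score that does not depend on the choice of eye, and the bias cancels in expectation between similar arms. This objection stands. It does not clear the secondary signs, because the only test the protocol names for them is a before-after test.

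**Baseline-adjusted arm comparison would largely solve it.** This is true for the expected bias between arms, and that comparison is part of the fix. But section 5.2 evaluates each group's change from baseline, and those changes stay inflated while the worst-eye rule remains.

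**The size is assumed.** A reader might take the upper rows of the table as the likely result. The 0.92 s figure needs every between-eye difference to be transient and no visit error shared. If most of the difference is lasting or the error is shared, the effect is slight. The protocol gives no data to decide between these cases.

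**NIBUT and Oxford class.** It is tempting to say that they are biased just as TBUT is. They are affected only as far as they correlate with TBUT error or break ties, and the protocol allows no figure for either.

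**Conclusion.** The point holds for within-arm, before-after testing of the secondary signs, mainly TBUT. It is conditional on the eye not being chosen on a separate earlier reading. The direction is fixed: towards improvement.

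The size is known only as a range, about 0.07 to 0.92 s against a relevant change of 1 s. The middle setting gives about 0.5 s, with roughly 22% false improvement at n = 32 and 28% at n = 43, against 2.5% nominal; the mild end gives under 4%. These figures rest on 2.3 s being the SD of change, on independent visit errors, and on assumed values of f and s.

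The change is worth making because it is cheap and the data are already planned. One further inference should be resisted: that with both eyes analysed, a within-arm improvement would show a drug effect. Without an untreated arm it cannot be separated from natural course or from the permitted lubricants.

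**What to change.** In section 11.3.1, replace the worst-eye rule for TBUT, NIBUT and Oxford class with the mean of the two eyes per patient, or with both eyes in a mixed model with a patient random effect. Compare the two arms with adjustment for the baseline value. Keep the worst eye as a sensitivity analysis and state which visit's reading defines it.

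Correct the opening sentence of the section as well. It places treatment as well as analysis on one eye, which does not fit an oral drug, and it should say that the eye rule does not apply to OSDI.

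Cost: a change of wording and slightly more analysis, with no new measurements. The results will be less directly comparable with publications that report the worst eye only.

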11.3.1.1 Primary efficacy endpoint

Paired t-test will be used to study OSDI. Chi-square is used to study clinically significant OSDI variation

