3. STUDY OBJECTIVES

3.1 Primary objective

To evaluate which of the protocols in the study (LCD Vs FPP) has the greatest impact on refractory MGD patient's symptoms (OSDI) on a six-month follow-up

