3.2 Secondary objective

Clinical Trial Protocol CPDOXY1

Comparison between continuous and pulsed oral doxycycline treatment protocols for refractory meibomian gland dysfunction - 9 months follow-up prospective study

To evaluate which of the protocols in the study (LCD Vs FPP) has a greater effect on patient's signs (NIBUT; TBUT, Oxford scale) on a six-month follow-up

To evaluate which protocol is related to the lower rate of adverse events

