4. STUDY DESIGN

4.1 Study Description

This spontaneous, prospective, non-randomized, parallel-group, phase IV study was conducted in compliance with the tenets of the Declaration of Helsinki.

All study participants were fully consented, and written informed consent was obtained.

This study included patients with refractory MGD. Refractory MGD is defined as symptomatic MGD (OSDI > 13 points) despite 2 months of first-line treatment with lacrimal substitutes 3 times per day and meibomian gland expression with warm compresses twice per day.

The study will consist of 3 visits: Visit 1(Baseline - day 0), Visit 2 (day 90 ± 5 - 3rd month), Visit 3 (day 180 ± 5 - 6 month). At each visit, patients will receive an OSDI questionnaire, NIBUT, type I Schirmer test and AS assessment, including TBUT, corneal staining (Oxford scale)

At baseline, eligible patients will be enrolled and treated with the assigned protocol. The investigators will assign the protocol (non-randomized) in a 1:1 ratio.

At Visit 2, NIBUT, TBUT, Oxford scale and OSDI improvement will be evaluated compared with Visit 1. Patients will be carefully asked about their compliance with the treatment. Patients who interrupted the treatment for adverse events or low compliance (<75% of the protocol adherence) will exit the study and be excluded from the analysis.

At Visit 3, the study population will be evaluated as done in Visit 2

The protocols in the study are the following:

- LCD (low-dose continuous protocol) - 50 mg of doxycycline for three months
- FPP (Full-dose pulsed protocol) - 100 mg of doxycycline for the first 15 days of the month for three months.

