11.3.3 Safety analysis

Chi-square is used for drop-out rates between groups

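### The paired t-test named for continuous OSDI and all the signs cannot compare the two regimens, and the sample size rests on the same before-after test

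*Protocol*

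**What the plan says.** The objectives are comparative. Section 3.1 reads "To evaluate which of the protocols in the study (LCD Vs FPP) has the greatest impact" on symptoms, and section 3.2 reads "To evaluate which of the protocols in the study (LCD Vs FPP) has a greater effect on" NIBUT, TBUT and the Oxford scale, both at six months. Section 4.1 describes a parallel-group study, so each patient receives one regimen only: "The investigators will assign the protocol (non-randomized) in a 1:1 ratio".

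The analysis is not comparative, or does not say that it is:

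- Section 11.3.1.1 (primary): "Paired t-test will be used to study OSDI. Chi-square is used to study clinically significant OSDI variation".
- Section 11.3.1.2 (secondary): "Paired t-test will be used to study the secondary variables".
- Section 11.2 (sample size): "The sample size estimate was based on a test for before-after studies using a paired t-test". The inputs are a 1 s change in Break-Up Time, SD 2.3 s, 2.5% one-tailed error and 80% power, giving 43 patients, raised to 65 for drop-out.
- Section 11.3.3 (safety) is the only place in section 11.3 where a contrast between arms is written out: "Chi-square is used for drop-out rates between groups".

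Sections 5.1 and 5.2 define the endpoints as changes from baseline in each of the two groups and state no contrast between them.

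**The concern.** A paired t-test needs two measurements on the same unit. Here the pairs can only be baseline and follow-up in one patient, because LCD and FPP patients are different people and nothing in the protocol matches them. The test therefore addresses whether patients changed, while the objectives ask which regimen changed them more. No between-arm test is named for continuous OSDI, NIBUT, TBUT or Oxford class.

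Two readings are possible, and both fail:

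- **Per arm.** Each regimen gets its own before-after p-value, and the reader is left to compare the two. One significant and one non-significant result is common even when the regimens are equal.
- **Pooled.** All patients are tested together, so the regimen does not enter the test.

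The comparative conclusion would then rest on the chi-square for patients improving by more than 7 OSDI points. Section 11.3.1.1 does not state its contrast, it discards information by dichotomising, and it is unadjusted although investigators choose each patient's regimen.

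**Working it through.** **Inputs.** From section 11.2: change 1 s, SD 2.3 s, one-sided 2.5%, 80% power, 43 evaluable, 65 enrolled. From section 4.1: 1:1 allocation, hence 32/33 if all 65 are analysed and 21/22 if 43 are.

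**Assumptions.** The 2.3 s is read as the SD of the change, as a paired formula requires. The protocol gives no between-arm difference, so 1 s is borrowed for illustration. It gives no OSDI SD, so power for OSDI cannot be computed and Break-Up Time stands in.

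**1. The plan's own figure.** n = (SD × (1.960 + 0.842) / change)² = (2.3 × 2.802 / 1)² = 41.5, so 42 by the normal approximation. The exact noncentral t gives 79.5% power at 43 and 80.5% at 44. The stated 43 is thus reproduced to within one patient, as the total for a single-group before-after test with no between-arm term.

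**2. Per-arm reading, both arms truly gaining 1 s.** The power p of the paired test within one arm is 0.475 (n=21), 0.494 (22), 0.664 (32) and 0.678 (33). The chance that exactly one arm is significant is p₁(1−p₂) + p₂(1−p₁):

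- 32/33: 0.664 × 0.322 + 0.678 × 0.336 = 0.44
- 21/22: 0.475 × 0.506 + 0.494 × 0.525 = 0.50

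**3. Pooled reading, average gain about 1 s.** 100,000 simulated trials per row, within-arm SD of change 2.3 s:

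| Analysed | Both arms gain 1 s | One arm gains 2 s, the other 0 s |
|---|---|---|
| 65 (32/33) | 93% significant | 90–91% significant |
| 43 (21/22) | 80% significant | 72–76% significant |

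The range in the last column depends on which arm has the extra patient. The result barely registers the difference that the trial is meant to find.

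**4. What a between-arm comparison of change could deliver.** Two-sample t-test, two-sided 5%, SE = 2.3 × √(1/n₁ + 1/n₂):

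| | 32/33 | 21/22 |
|---|---|---|
| SE | 0.571 s | 0.702 s |
| 95% CI half-width (t × SE) | 1.998 × 0.571 = 1.14 s | 2.020 × 0.702 = 1.42 s |
| Power for a 1 s difference | 41% | 29% |
| Difference detectable with 80% power | 1.62 s (0.71 SD) | 2.01 s (0.88 SD) |

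For 80% power at a 1 s difference, 84 per arm gives 79.99% and 85 per arm gives 80.5%. The SD-unit figures are the ones that carry over to OSDI, in units of the SD of OSDI change.

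**5. Sensitivity to the SD.** If 2.3 s is instead the SD at one visit, the SD of change is 2.3 × √(2(1−ρ)), where ρ is the baseline/follow-up correlation. For ρ from 0.3 to 0.7 this runs from 2.72 s to 1.78 s, and power at 32/33 for 1 s runs from 31% to 61%. Every value stays below 80%.

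**6. Effect of baseline adjustment.** With equal SDs at both visits, the ANCOVA residual SD is 2.3 × √((1+ρ)/2), which is 1.85 s at ρ = 0.3 and 2.12 s at ρ = 0.7. Power for 1 s is then 57% to 46% at 32/33 and 41% to 33% at 21/22, provided the covariates are balanced between the arms.

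**The case against.** The strongest reply is that a between-arm test of the primary objective does exist. Patients improving by more than 7 OSDI points are one of the two primary endpoints in section 5.1, and a chi-square on responders in two groups is most naturally read as LCD versus FPP. That is fair, and the missing contrast may be no more than brevity. But it covers one of the two primary endpoints and none of the signs, so the secondary efficacy objective is left with no comparative test.

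It can also be said that the paired test suits sections 5.1 and 5.2, which speak of change from baseline in each group. This makes the per-arm reading the likelier one and the pooled simulation the less relevant one. It does not help the plan: the mismatch is then between the objectives on one side and the endpoints and analysis on the other.

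Three cautions about the numbers stand:

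- The 1 s is a before-after change in the protocol, so the 41% and 29% are illustrative. The detectable differences and CI widths do not depend on it.
- The 21/22 figures apply only if the section 4.1 exclusions reduce the analysed set. Under the intent-to-treat analysis with last observation carried forward in section 11.1.2, the 32/33 figures are closer.
- The ANCOVA gain is not assured when investigators choose the regimen. If the covariates explained 20% of the assignment (an assumption), power at 32/33 would be about 39% to 48%, and the lower end falls below the unadjusted 41%.

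Leaving the matter to a statistical analysis plan is no answer, because the protocol itself names the test and sizes the study on it.

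**Conclusion.** The concern holds and must be fixed. For continuous OSDI and every sign, the named test cannot answer the stated objective. That conclusion follows from the design and depends on none of the figures.

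The figures show what is at stake. Reading two within-arm p-values against each other would suggest a difference between equal regimens in roughly 44% to 50% of trials, if each arm truly gains 1 s with an SD of change of 2.3 s. The 80% power in section 11.2 belongs to a before-after change in Break-Up Time and says nothing about LCD versus FPP. With 43 to 65 patients analysed, only a between-arm difference of about 0.7 to 0.9 SD of change is detectable with 80% power. Power for OSDI itself remains unknown until an OSDI SD is supplied.

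**What to change.** - **Section 11.3.1.1.** Name as the primary analysis the LCD minus FPP difference in OSDI change at Visit 3 (month 6), with a 95% CI. ANCOVA is a suitable method, adjusted for baseline OSDI and, because allocation is not random, for a short pre-stated list of baseline values already collected, such as TBUT. State that the >7-point chi-square compares LCD with FPP. Treating it as supportive is advisable; since section 5.1 lists it as primary, that section must then be changed to match.
- **Sections 5.1 and 5.2.** Add the between-arm contrast to the endpoint wording.
- **Section 11.3.1.2.** Use between-arm analyses adjusted for baseline, with an ordinal method for Oxford class. Keep paired tests as description only.
- **Section 11.2.** State that 43, 65 and 80% power refer to a before-after Break-Up Time change. Add the between-arm OSDI difference and CI width achievable with 65 enrolled and 43 evaluable, using an OSDI SD with its source.

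The cost is wording and a few lines of analysis code, with no new data. The drawback is that low precision becomes visible: 80% power for a 1 s difference would need about 85 evaluable per arm unadjusted, against 32 or 33 now. Either the sample size is raised, or the result is presented as an estimate with a wide interval. Adjustment removes only measured confounding.

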11.3.1.2 Secondary efficacy endpoints

Paired t-test will be used to study the secondary variables.

11.3.2 Compliance analysis

Patient that stopped or missed more than 25% of the assumptions (ex more than 28 cp for LCP or more than 14 cp for FPP)

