7.3 Treatment Dosage, administration, and compliance

Please note the following information:

The dosage will vary depending on the treatment plan prescribed for the patient. This may involve taking 50 mg (half a tablet) daily for three months, or 100 mg (one tablet) for 15 days each month for three months.

Patients will take the medication at home without medical supervision. However, they will be able to contact the medical staff involved in the study if they have any questions or suspect any adverse events.

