11.1.2 Intent-to-Treat (ITT) Analysis Set

Signs and symptoms will be analyzed using an intent-to-treat approach. In case of missing data, the last observation available will be carried forward. This will be the primary analysis.

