14.7 Study timetable and end of study

	Visit 1 (day 0)	Visit 2 (day 90)	Visit 3 (day 180)
Verify inclusion and exclusion criteria	X		
Informed consent signature	X		
OSDI questionnaire	X	X	X
NIBUT	X	X	X
AS assessment of blepharitis and hyperemia	X	X	X
TBUT	X	X	X
Adherence to study treatments		X	
Prescribe study drug	X		

Clinical Trial Protocol CPDOXY1

Comparison between continuous and pulsed oral doxycycline treatment protocols for refractory meibomian gland dysfunction - 9 months follow-up prospective study

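### The example counts for non-compliance (more than 28 for LCD, more than 14 for FPP) are about 31% of the scheduled intakes, not the 25% they illustrate

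*Protocol*

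**What the plan says.** Section 11.3.2 of the protocol defines non-compliance as having stopped, or having "missed more than 25% of the assumptions (ex more than 28 cp for LCP or more than 14 cp for FPP". Here *assumptions* evidently means intakes, *LCP* is the arm called LCD elsewhere, and *cp* is not defined.

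The other relevant statements in the protocol are:

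- **Schedule (7.3):** "50 mg (half a tablet) daily for three months, or 100 mg (one tablet) for 15 days each month for three months". Section 4.1 describes the pulsed arm in the same terms: "100 mg of doxycycline for the first 15 days of the month for three months".
- **Consequence (4.1):** patients with "low compliance (<75% of the protocol adherence) will exit the study and be excluded from the analysis".
- **When and how it is checked:** the timetable in 14.7 marks "Adherence to study treatments" at Visit 2 only, and 4.1 places that visit at "Visit 2 (day 90 ± 5 - 3rd month"). Section 7.4 has the compliance rate worked out from the blisters that patients return at that visit.
- **What depends on it:** the primary objective (3.1) concerns "symptoms (OSDI) on a six-month follow-up". For the intent-to-treat set, 11.1.2 states: "In case of missing data, the last observation available will be carried forward. This will be the primary analysis".

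**The concern.** Sections 4.1 and 11.3.2 give the same percentage limit: adherence below 75% is the same as more than 25% missed. The bracketed counts in 11.3.2 are the only place where the limit appears as a number of units, and units are what is counted from returned blisters. If the counts stand for a different percentage, the protocol holds two rules for who is non-compliant.

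A patient who falls between the two rules stays or leaves at Visit 2 according to which one the site applies. If the intent-to-treat rule in 11.1.2 governs, that decides whether the patient's six-month OSDI is observed or carried forward from Visit 2. If the exclusion in 4.1 is taken literally, it decides whether the patient is analysed at all.

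**Working it through.** **Inputs**

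- LCD: half a 100 mg tablet daily for three months (7.2, 7.3), about 90 intakes = 45 tablets = 4500 mg.
- FPP: one tablet on 15 days a month for three months (7.3), 3 × 15 = 45 intakes = 45 tablets = 4500 mg.
- Limit: more than 25% missed (11.3.2; equivalent to the 75% in 4.1).
- Example counts: 28 and 14 (11.3.2).

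**Step 1. What 25% gives.** Limit = 0.25 × scheduled intakes.

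- LCD: 0.25 × 90 = 22.5, so 23 or more missed.
- FPP: 0.25 × 45 = 11.25, so 12 or more missed.

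The printed 28 and 14 are not reproduced.

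**Step 2. What the printed counts imply.** Share = count / scheduled units.

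| Arm | *cp* = one intake | *cp* = one whole tablet |
|---|---|---|
| LCD | 28/90 = 31.1% | 28/45 = 62.2% |
| FPP | 14/45 = 31.1% | 14/45 = 31.1% |

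In FPP one intake is one tablet, so the undefined unit cannot explain the difference there. Since the rule says more than 28 and more than 14, the first counts that trigger it are 29/90 = 32.2% and 15/45 = 33.3%.

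**Step 3. Which unit is meant.** The intake reading is likelier. The noun being counted is intakes, and that reading gives the same missed dose in both arms: 28 × 50 mg = 14 × 100 mg = 1400 mg, and 1400/4500 = 31.1%.

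**Step 4. Can the treatment length explain it?** For 28 and 14 to be 25%, the schedules would need 28/0.25 = 112 and 14/0.25 = 56 units.

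- LCD over the Visit 2 window of 85 to 95 days: 28/85 = 32.9% to 28/95 = 29.5%. More than 25% would start at 22 of 85 or 24 of 95.
- FPP, counting months from the start of treatment: the third pulse ends about day 60 + 15 = 75, before the earliest Visit 2 at day 85, so the denominator stays 45. A pulse cut short would only raise the share further above 25%.

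No reading reaches 25%.

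**Step 5. Who is classed differently (intake reading).**

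- LCD: 23 to 28 missed, six counts, adherence 67/90 = 74.4% down to 62/90 = 68.9%.
- FPP: 12 to 14 missed, three counts, adherence 33/45 = 73.3% down to 31/45 = 68.9%.

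On the whole-tablet reading the FPP band is the same. The LCD band widens to 11.5 to 28 of 45 tablets, which is 25.6% to 62.2% missed.

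**Step 6. Number of patients.** The protocol gives no distribution of adherence. Assuming that 2% to 10% of the 65 patients fall in the band: 0.02 × 65 = 1.3 to 0.10 × 65 = 6.5, about 1 to 7 patients.

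**The case against.** The strongest reply is that the operative rule is clear. The percentage is given twice and consistently, the counts are in brackets and marked as examples, and 7.4 asks for a compliance rate, which a site would naturally compare with 75%. On that view the counts are a slip with no effect. It can be added that the two counts agree with each other on the intake reading, so they may reflect a deliberately looser limit; that adherence is checked when the Visit 2 OSDI is taken anyway, so under intent-to-treat only the Visit 3 value can change; and that nothing in the protocol supports any particular share of patients in the disputed band, which could be empty.

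Much of this stands as a limit on size. The effect is small, the patient numbers are an assumption, and the whole-tablet reading is the less likely one. It does not remove the mismatch. An example has to satisfy the rule it illustrates, and here a patient can breach the percentage without reaching the count. If a looser limit was meant, the percentage is wrong in two places instead.

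The consequence also depends on how 4.1 (exclusion from the analysis) and 11.1.2 (intent-to-treat with carry-forward) are read together. That is a separate matter, and the literal reading of 4.1 would make the consequence larger, not smaller.

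**Conclusion.** The point holds: section 11.3.2 is wrong as written. Its counts correspond to 31.1% missed in both arms on the intake reading, or 62.2% in LCD and 31.1% in FPP on the whole-tablet reading, against a stated 25%. The FPP figure establishes this without any assumption about the unit.

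The conclusion rests on a three-month course of about 90 days and on the schedules in 7.3; moving the LCD course between 85 and 95 days does not change it. The practical effect is confined to patients who miss 23 to 28 LCD or 12 to 14 FPP intakes, about 1 to 7 of 65 under the assumed 2% to 10%. It should be corrected because the rule removes patients from the study, but it does not by itself threaten the primary analysis.

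**What to change.** Reconcile the counts in 11.3.2 with the percentage given there and in 4.1. State the limit as a share of each patient's prescribed intakes and name the unit: a half-tablet intake for LCD, a one-tablet intake for FPP. If counts are kept as illustrations, the protocol's own 25% over a 90-day course converts to 23 or more of 90 LCD intakes and 12 or more of 45 FPP intakes. If the sponsor in fact intended the printed counts, the percentage has to be changed in both sections instead. *LCP* should read LCD, as a copy-edit.

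The cost is a one-line correction in 11.3.2 (plus 4.1 only if the percentage is the part that changes). No additional data or patients are needed.
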